4.1. Overall Design

This is a Phase 2, proof-of-concept, placebo-controlled, double-blind, randomized study in adult participants with moderately to severely active RA who have had an inadequate response to csDMARDs, or to bDMARDs/tsDMARDs. Participants will be administered LY3462817 or placebo IV Q4W.

Screening Period (Visit 1, Days -42 to -1)

Participants will sign the informed consent document(s) at Visit 1, prior to completion of any procedures. Participants will be evaluated for study eligibility \leq 42 days prior to the baseline visit (Visit 2).

Period 1: Double-blind Treatment (Visits 2 to 6; 12 weeks)

At the baseline visit (Visit 2), participants who fulfill the eligibility criteria will be randomized to receive LY3462817 700 mg, LY3462817 300 mg, or placebo in an allocation ratio of 2:1:1.

The double-blind treatment period will establish the clinical efficacy and safety of LY3462817. The study will be evaluated for the primary objective at the end of the double-blind treatment period.

Period 2 (Visits 6 to 10; 12 weeks)

Data from a Study KDAC interim analysis that includes Week 12 data from participants in the KDAC 700-mg cohort, must be reviewed prior to a participant proceeding to Period 2 in Study KDAD.

At Week 14, participants will be evaluated for clinical benefit.

Participants assigned to LY3462817 at baseline, and achieving low disease activity (CDAI \leq 10) at Week 14 will continue to receive LY3462817 at the randomized dose through Week 24 to assess safety and tolerability and evaluate efficacy.

All other participants at Week 14, regardless of baseline treatment assignment, will stop study drug infusions and should receive standard of care treatment at the investigator's discretion.

Posttreatment Safety Follow-up Period (Visits V801 and 802; 12 weeks)

Following Period 2, participants will be followed posttreatment for 12 weeks to assess safety, study drug exposure, and clinical disease activity measures. Participants who discontinue the study intervention per Section 7 will have their last visit at 12 weeks from the last administration of the study intervention.

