Participant Disposition	
A detailed description of participant disposition will be provided, including a summary of the number and percentage of participants entered into the study and randomized, and number and percentage of participants who complete the study or discontinue, both overall and by reason for discontinuation. A summary of important protocol deviations will be provided.

Participant Characteristics	
Demographic data are collected and responded to demonstrate that the study population represents the target patient population. A summary of baseline participant characteristics, historical diagnoses, preexisting conditions, and prior therapies will be reported by treatment group using descriptive statistics. Other participant characteristics will be summarized by treatment group as deemed appropriate.

Concomitant Therapy	
Previous and concomitant medications will be summarized by treatment group and will be presented by Anatomical Therapeutic Chemical drug classes using the latest version of the WHO drug dictionary.

Treatment Compliance	No analyses are planned to assess treatment compliance, given that participants will receive study intervention directly from the investigator or designee at the study site, under medical supervision.
----------------------	--

Summary statistics for continuous measures will include sample size, mean, standard deviation, median, minimum, and maximum.

For categorical data, summary statistics will include sample size, frequency, and percentages. Percentages will be rounded to one decimal place. Unless otherwise specified, Fisher's exact test will be used for making treatment comparisons.

All statistical tests of treatment effects will be performed at two-sided significance levels of 0.05 and 0.10, respectively, unless otherwise specified. All p-values will be presented to three decimal places.

The Treatment Period is defined as the combination of Period 1 with double-blind treatment and Period 2.

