The baseline period is defined as Visit 1 through pre-dose Visit 2. The Double-blind Treatment Period starts after the first injection of study treatment at Visit 2 (Week 0) and ends on the date of Visit 6 (Week 12) or the early discontinuation visit. The Period 2 starts after the date of Visit 6 (Week 12) or the early discontinuation visit and lasts up to 24 weeks following the last injection of study treatment. Additional follow-up beyond 24 weeks may be deemed necessary and, if so, any data collected will be considered as part of Period 2.

Unless otherwise specified, baseline for the Treatment Period is defined as the last non-missing assessment on or prior to the date of the first injection of study treatment, scheduled to be given at the end of Visit 2. Any assessment collected after the first injection through the date of the Week 12 or early discontinuation visit is defined as post-baseline for the Treatment Period.

Data collected at early discontinuation visits will be mapped to the next planned visit number for that patient. For by-visit summaries, only visits in which a measure was scheduled to be collected will be summarized.

Summaries of safety data collected during Period 2 will be presented separately. Unless otherwise specified, follow-up baseline is defined as the last non-missing assessment on or prior to the date of Week 12 or the date of the early discontinuation visit.

Change from baseline will be calculated as the post-baseline value minus the baseline value. Percent change from baseline is defined as $(100 \times (\text{post-baseline} - \text{baseline}) / \text{baseline})$. If all baseline values are missing for a particular variable, the change from baseline and percent change from baseline will not be calculated.

The statistical analyses of efficacy, health outcomes, and safety measures will be performed using SAS Version 9.4 or higher. Lilly will be responsible for conducting analyses.

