4.6.2. Adverse Events

A treatment-emergent adverse event (TEAE) is defined as an event that first occurred or worsened in severity after baseline, with baseline defined as all pre-existing conditions recorded at Visit 1 and any AEs recorded before the first dose of study intervention (that is, during the interval between Visits 1 and 2 and recorded with the time of onset before the first dose of study intervention). The MedDRA Lowest Level Term (LLT) will be used in the treatment-emergent computation. The maximum severity for each LLT before the first injection will be used as baseline. Start date of adverse events will be compared with date of first injection and the date of Visit 10 (Week 24) to determine whether an adverse event is treatment-emergent. Should there be insufficient data for adverse event start date or severity to make this comparison; the adverse event will be considered treatment-emergent.

TEAEs will be coded according to established Medical Dictionary for Regulatory Activities (MedDRA) terms and summarized by MedDRA System Organ Class (SOC) and Preferred Term.

An overview of adverse events will summarize the percentage of patients experiencing deaths, SAEs, AEs reported as reason for discontinuation, TEAEs, and AEs possibly related to study treatment.

The frequency and percentage of patients with the following will be summarized using MedDRA Preferred Term nested within SOC.

- TEAEs
- TEAEs by maximum severity
- TEAEs related to study intervention
- TEAEs leading to study discontinuation
- SAEs including death
- SAEs by maximum severity
- SAEs related to study intervention
- Deaths
- AE of Special Interests (AESIs)

Events will be sorted alphabetically by SOC and then by decreasing total frequency within SOC. For incidence counts, each patient will be counted only once within each Preferred Term and within each SOC. Percentages will be based on the number of patients in a particular treatment arm. For events that are gender-specific, the denominator and computation of the percentage will include only patients from the given gender.

Adverse events of special interest will be identified by a standardized MedDRA query or a Lilly-defined MedDRA preferred term listing.

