The frequency and percentage of patients with treatment-emergent abnormal, high, or low laboratory results at any time will be summarized. Similarly, the frequency and percentage of patients with treatment-emergent abnormal, high, or low laboratory results at Week 24 endpoint will be summarized. A treatment-emergent abnormal result is defined as a change from normal at all baseline visits to abnormal at any time during the Treatment Period. A treatment-emergent high result is defined as a change from a value less than or equal to the high limit at all baseline visits to a value greater than the high limit at any time during the Treatment Period. A treatment-emergent low result is defined as a change from a value greater than or equal to the low limit at all baseline visits to a value less than the low limit at any time during the Treatment Period. For each laboratory test, only patients who were normal (i.e., less than or equal to the high limit for treatment-emergent high, or greater than or equal to the low limit for treatment-emergent low) at all baseline visits and who have at least one non-missing post-baseline result will be included in the denominator when computing the percentages of patients with treatment-emergent abnormal, high, or low results. Scheduled visits, unscheduled visits, and repeat measurements will be included. Covance Reference Ranges will be used to define the low and high limits.

Shifts from baseline to maximum post-baseline result during the Treatment Period for ALT, AST, and total bilirubin will be provided for the following categories:

- ALT; $\leq 1 \times \text{ULN}$, $> 1 \text{ to } \leq 3 \times \text{ULN}$, $> 3 \text{ to } \leq 5 \times \text{ULN}$, $> 5 \text{ to } \leq 10 \times \text{ULN}$, and $> 10 \times \text{ULN}$.

- AST; $\leq 1 \times \text{ULN}$, > 1 to $\leq 3 \times \text{ULN}$, > 3 to $\leq 5 \times \text{ULN}$, > 5 to $\leq 10 \times \text{ULN}$, and $> 10 \times \text{ULN}$.
- Total bilirubin; $\leq 1 \times \text{ULN}$, > 1 to $\leq 1.5 \times \text{ULN}$, $> 1.5 \times \text{ULN}$.

Shifts from baseline to minimum post-baseline result during the Treatment Period for neutrophils, lymphocytes, and leukocytes will be provided for the following categories:

- Neutrophils; $< \text{LLN}$ to $\geq 1.5 \times 10^9/\text{L}$, $< 1.5 \times 10^9/\text{L}$ to $\geq 1.0 \times 10^9/\text{L}$, $< 1.0 \times 10^9/\text{L}$ to $\geq 0.5 \times 10^9/\text{L}$, and $< 0.5 \times 10^9/\text{L}$.

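### SAP 4.1 gives conflicting ends for Period 2 and the Treatment Period, and one of them puts follow-up laboratory results under a treatment-emergent label

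*SAP*

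**What the plan says.** The documents give several ends for the same period.

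- **Protocol 4.1 and SAP 1.2.** Both set "Period 2 (Visits 6 to 10; 12 weeks" and then a separate "Posttreatment Safety Follow-up Period (Visits V801 and 802; 12 weeks". The protocol states the purpose of the latter: "Following Period 2, participants will be followed posttreatment for 12 weeks to assess safety, study drug exposure, and clinical disease activity measures".
- **SAP 4.1, Treatment Period.** "The Treatment Period is defined as the combination of Period 1 with double-blind treatment and Period 2".
- **SAP 4.1, Period 2.** It begins after Visit 6 or the early-discontinuation visit "and lasts up to 24 weeks following the last injection of study treatment". The next sentence leaves the end open: "Additional follow-up beyond 24 weeks may be deemed necessary and, if so, any data collected will be considered as part of Period 2".
- **SAP 4.1, post-baseline.** The following paragraph closes post-baseline for the Treatment Period at the Week 12 or early-discontinuation visit.
- **SAP 4.6.2, adverse events.** "Start date of adverse events will be compared with date of first injection and the date of Visit 10 (Week 24" to decide whether an event is treatment-emergent. SAP 4.6.2.6 ends the C-SSRS window at Visit 10 or early discontinuation.
- **SAP 4.6.3, laboratory.** A treatment-emergent high result is a change from at or below the limit at all baseline visits "to a value greater than the high limit at any time during the Treatment Period". The abnormal and low definitions, the minimum and maximum changes, and the ALT, AST, bilirubin and cell-count shift tables use the same period. SAP 4.6.5 does likewise for vital signs.

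**The concern.** Safety is a listed secondary objective, and the treatment-emergent laboratory tables are part of how it is answered. If the Period 2 sentence governs, the follow-up is absorbed into the Treatment Period. Results from participants long off study drug, most of them directed to standard of care from Week 14, would be tabulated as treatment-emergent on the randomized arm. The adverse-event tables beside them would stop at Week 24, so one label would cover two windows.

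Two further consequences follow from the same wording. Period 2 starts after an early-discontinuation visit, so someone who stops at Week 4 contributes Period 2 safety data without having reached the protocol's Period 2. Also, Protocol 9.4.7 plans summaries of follow-up emergent adverse events. SAP 4.6.2 lists none, although SAP 4.9 reports no change from the protocol. With no follow-up period defined in SAP 4.1, that planned summary has no data window.

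**Working it through.** **Inputs.** From the Schedule of Activities (Protocol 1.3): V6 = Day 84, V10 = Day 168, V801 = Day 196, V802 = Day 252, each ±7 days. Infusions at Weeks 16 to 24 go only to LY3462817 participants with low disease activity at Week 14, so for everyone else the last planned infusion is at Week 12. Terminal half-life is about 10 days (Protocol 2.2).

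**1. Reproduce the stated lengths.** Period 2 = (168 − 84)/7 = 12 weeks. Follow-up = (252 − 168)/7 = 12 weeks. Both match Protocol 4.1 and SAP 1.2.

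**2. Apply the SAP 4.1 Period 2 sentence (24 weeks = 168 days).**

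| Last infusion | SAP Period 2 ends | V801 after last infusion | V802 after last infusion |
|---|---|---|---|
| Week 12 (Day 84) | 84 + 168 = Day 252, Week 36 | 112 days, 16 weeks, about 11 half-lives | 168 days, 24 weeks, about 17 half-lives |
| Week 24 (Day 168) | 168 + 168 = Day 336, Week 48 | 28 days, 4 weeks, about 3 half-lives | 84 days, 12 weeks, about 8 half-lives |

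In both groups the whole scheduled follow-up lies inside the SAP's Period 2.

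**3. Count the scheduled measurements.** Hematology and chemistry are marked post-baseline at Weeks 4, 8, 12, 14, 16, 20 and 24 (7 draws), and again at V801 and V802 (9 draws). The vital-signs row is marked only through V10 and the early-termination visit. Follow-up therefore adds no scheduled vital signs, only unscheduled ones.

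**4. Size of the background shift.** The documents give no per-draw rate, so assume each draw has probability q of a chance abnormal value, independently. The rate over n draws is 1 − (1 − q)^n.

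| q (assumed) | 7 draws | 9 draws | Added, arm of 20 | Added, arm of 40 |
|---|---|---|---|---|
| 1% | 1 − 0.99^7 = 6.8% | 1 − 0.99^9 = 8.6% | about 0.4 | about 0.7 |
| 2% | 1 − 0.98^7 = 13.2% | 1 − 0.98^9 = 16.6% | about 0.7 | about 1.4 |
| 5% | 1 − 0.95^7 = 30.2% | 1 − 0.95^9 = 37.0% | about 1.4 | about 2.7 |

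The last two columns are participants per laboratory test, taking every participant as normal at baseline and attending all visits.

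**5. Effect on a between-arm difference.** Let the risks to Week 24 be p1 and p0, and give both arms the same q at the two added draws. Each arm's risk becomes 1 − (1 − p)(1 − q)^2, so the difference becomes (p1 − p0)(1 − q)^2. The multiplier is 0.98^2 = 0.96 at 2%, 0.99^2 = 0.98 at 1%, and 0.95^2 = 0.90 at 5%.

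**6. What a Visit 10 end changes.** For participants last dosed at Week 12, the longest gap from last infusion to a scheduled counted draw falls from 24 weeks to 12. The draws at Weeks 16, 20 and 24 (4, 8 and 12 weeks after that infusion) remain, because they lie in the protocol's own Period 2. Of the five draws from Week 16 onward, the change removes two.

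**The case against.** The best defense is that the SAP never clearly chooses to count follow-up as treatment. SAP 1.2 keeps the follow-up separate. SAP 4.6.2.1 notes a Treatment Period planned for 24 weeks. SAP 4.6.2.3 names a post-treatment follow-up period, and the Week 12 post-baseline sentence points to a shorter window still. A reader might infer that the sponsor decided to fold follow-up into treatment. The documents do not support that: they contradict one another. The contradiction still needs correcting, because a programmer following the Period 2 sentence would be following the plan.

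SAP 4.1 also says Period 2 safety summaries will be presented separately. This helps little: the laboratory definitions refer to the combined Treatment Period, and under the SAP's definition Period 2 itself contains the follow-up.

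Three other objections stand in full.

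- Treatment-emergent adverse events are bounded at Visit 10 and are unaffected.
- The 24-week gap applies to participants last dosed at Week 12. For those infused through Week 24 the gap at V802 is 12 weeks, and the protocol schedules the last visit for those who discontinue study intervention 12 weeks after their last administration.
- The per-draw rates are assumptions, and positive correlation between draws in one person would generally make the increment smaller.

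**Conclusion.** SAP 4.1 conflicts with the protocol, with SAP 1.2 and with itself on when Period 2 and the Treatment Period end. Depending on the sentence applied, the laboratory window closes at Week 12, 24, 36 or 48. Under the Period 2 sentence, 9 scheduled hematology and chemistry draws count instead of 7, and the laboratory window differs from the adverse-event window under the same label.

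The size is modest. At an assumed 2% per independent draw, the background rate per test moves from 13.2% to 16.6%, and a between-arm difference is multiplied by about 0.96. A reader might conclude that on-drug safety differences would be hidden, or that the vital-sign tables are affected as much as the laboratory ones. Neither follows: the dilution is mild across the assumed range (0.98 to 0.90), and no vital signs are scheduled at V801 or V802. The primary analysis is not touched. The correction is still worth making, because the rule is wrong as written and easily put right.

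**What to change.** In SAP 4.1:

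1. End Period 2 and the Treatment Period on the date of Visit 10, or of the early-discontinuation visit if that comes first. Start Period 2 only for participants who reach it.
2. Replace the Week 12 post-baseline sentence so that it matches this window. Otherwise the contradiction remains.
3. Assign V801, V802 and any later data, including data after an early-discontinuation visit, to a separate Post-treatment Follow-up Period with its own summaries. That period also gives the protocol's follow-up emergent adverse-event summary a data window.
4. State that Week 16 to 24 results in participants already off study drug stay in the Treatment Period under this definition, and flag them so that they can be identified.

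The cost is SAP wording, one dataset flag and a small extra table. There is one trade-off: for participants infused at Week 24, V801 comes only 28 days after that infusion and would be reported as follow-up. The follow-up table should therefore be read alongside the treatment table. The adverse-event rule already makes the same cut.

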10.6. Appendix 6: Recommended Laboratory Testing for Hypersensitivity Events

Laboratory assessments should be performed if the participant experiences generalized urticaria or if anaphylaxis is suspected:

- Collect sample after the participant has been stabilized, and within 1 to 2 hours of the event; however, samples may be obtained as late as 12 hours after the event as analytes can remain altered for an extended period of time. Record the time at which the sample was collected.
- Obtain a follow-up sample at the next regularly scheduled visit or after 4 weeks, whichever is later.

Hypersensitivity Tests	Notes
	Selected test may be obtained in the event of anaphylaxis or systemic allergic/hypersensitivity reactions.
LY3462817 antidrug antibodies (immunogenicity/ADA)	Assayed by Lilly-designated laboratory. Results will not be provided to the investigative sites.
LY3462817 concentrations (PK)	Assayed by Lilly-designated laboratory. Results will not be provided to the investigative sites.
Tryptase	
Assayed by Lilly-designated laboratory. Results will not be provided to the investigative sites.
 
Note: If a tryptase sample is obtained more than 2 hours after the event (i.e., within 2 to 12 hours), or is not obtained because more than 12 hours have lapsed since the event, obtain urine sample for N-methylhistamine testing. Note that for tryptase serum samples obtained within 2 to 12 hours of the event, urine N-methylhistamine testing is performed in addition to tryptase testing. Collect the first void urine following the event. Obtain a follow-up urine for N-methylhistamine testing at the next regularly scheduled visit or after 4 weeks, whichever is later.

N-methylhistamine	Assayed by Lilly-designated laboratory. Results will not be provided to the investigative sites.
Drug-specific IgE	
Will be performed if a validated assay is available.
 
Assayed by Lilly-designated laboratory. Results will not be provided to the investigative sites.

Basophil activation test	
Will be performed if a validated assay is available.
 
Assayed by Lilly-designated laboratory. Results will not be provided to the investigative sites.
 
NOTE: The basophil activation test is an in vitro cell-based assay that only requires a serum sample. It is a surrogate assay for drug-specific IgE but is not specific for IgE.

Complement (C3, C3a, and C5a)	Assayed by Lilly-designated laboratory. Results will not be provided to the investigative sites.

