4.1. General Considerations

The independent variable, previous RA therapy population, is defined as only csDMARD experienced or bDMARD/tsDMARD experienced participants. Unless otherwise indicated in the statistical analysis plan (SAP), the analyses will be conducted as follows:

Analysis for	Description
Primary and secondary endpoint analyses comparing LY3462817 to placebo	Tested at a 2-sided level of 0.05 for frequentist analyses
Adjustments for multiplicity	None to be performed
Baseline	Defined as the last available value before the first dose of study intervention for both efficacy and safety analyses. In most cases, this value will be what is recorded at the randomization visit (Visit 2).
Change from baseline	Will be calculated as the visit value of interest minus the baseline value.
Efficacy and patient-reported outcome (PRO) analysis	Analysis models may contain the independent variables such as treatment group, baseline disease activity, and previous RA therapy population. Endpoint analyses will use the FAS unless otherwise specified.
Dichotomous responder endpoints	Missing data will be imputed using the nonresponder imputation (NRI) method. Will be analyzed using a logistic regression model with treatment group, baseline disease activity, and previous RA therapy population as model covariates.
NRI analysis	Participants will be considered nonresponders if: 
 • they do not meet all the clinical response criteria • they are noncompliant with concomitant medication rules

	
 • they permanently discontinue study intervention at any time before the end of the treatment period for any reason, or • they are randomized and do not have at least 1 postbaseline observation.
Continuous efficacy endpoints	
Mixed-effects model for repeated measures (MMRM) will be used.
 
The MMRM model will include treatment, strata (previous RA therapy population), baseline value, visit, treatment-by-visit interaction in the model as fixed factors, and patient as a random factor.
 
An unstructured covariance matrix will be used to model the within-subject errors. If this analysis fails to converge, other structures will be tested (in this order: Toeplitz, Autoregressive with heterogeneity, and compound symmetry.).
 
The Kenward-Roger approximation will be used to estimate denominator degrees of freedom. Significance tests will be based on least squares means and Type III tests.

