4.6.3. Clinical Laboratory Evaluation

All numerical laboratory tests for serum chemistries, fasting lipids, hematology, RF and anti-CCP antibodies, CRP, and ESR will be summarized by treatment arm for baseline, all post-baseline visits during the Treatment Period, Week 24 endpoint, and change from baseline to post-baseline visits and Week 24 endpoint.

Urinalysis, TSH, and T4 are collected at screening only, and will appear in data listings.

Summary of B-cells, immunoglobulins, immunogenicity tests, and BAFF levels are described in the subsections below.

Change from baseline to Week 24 endpoint in laboratory tests will be summarized for patients who have both a baseline and at least one post-baseline result. For all laboratory tests except CD3-CD20+B cells counts, baseline is defined as the last non-missing result on or prior to the date of the first injection of study treatment.

Change from the minimum value on or prior to the date of the first injection of study treatment to the minimum value during the Treatment Period in laboratory tests will be summarized for patients who have both a baseline and at least one post-baseline result. Similarly, change from the maximum value on or prior to the date of the first injection of study treatment to the maximum value during the Treatment Period in laboratory tests will be summarized for patients who have both a baseline and at least one post-baseline result. Scheduled visits, unscheduled visits, and repeat measurements will be included.

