4.6.4.2. Serum Immunoglobulin (Ig) Levels and Cytokines

Serum Ig levels, including IgA, IgG and IgM, and cytokines will be summarized by treatment arm for baseline, all post-baseline visits, Week 24 endpoint, and both change from baseline and percent change from baseline to each post-baseline visit and Week 24 endpoint. Baseline is defined as the last non-missing result on or prior to the date of the first injection of study treatment.

The change from baseline in Ig levels and cytokines to each post-baseline visit will also be summarized by treatment arm and whether the patient has positive anti-drug antibodies (ADAs) (yes or no) at that visit.

For each parameter, the mean percentage change from baseline over time (in weeks) will be summarized graphically by treatment arm.

Shift tables will be produced showing the frequency and percentage of patients with a minimum post-baseline result during the Treatment Period in each relevant category, by treatment arm and baseline result. Such shift tables will be produced for the following parameters and categories:

- IgA: < LLN to $\geq 0.35\text{g/L}$, and $<0.35\text{g/L}$.
- IgG: < LLN to $\geq 2.82\text{g/L}$, and $<2.82\text{g/L}$.
- IgM: < LLN to $\geq 0.20\text{g/L}$, and $<0.20\text{g/L}$.

The change from baseline to Weeks 12 and 24 endpoints in Ig levels and cytokines will also be plotted against the change from baseline to Weeks 12 and 24 endpoints in the following variables:

- ACR20, ACR50, DAS28-CRP, HAQ-DI,

The change from baseline to Week 24 endpoint in Ig levels and cytokines will also be plotted against the total number of treatment-emergent infectious adverse events during the Treatment Period. Treatment arms will be identified using different symbols in the scatter plots.

A by-patient listing of serum Ig levels and cytokines during the Treatment Period will be provided.

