4.6.5. Vital Signs and Other Physical Findings

Vital signs and physical characteristics to be summarized include temperature, sitting heart rate, sitting blood pressure (systolic and diastolic), weight, and BMI. Vital signs and physical characteristics will be summarized by treatment arm for baseline, all post-baseline visits, Week 24 endpoint, and change from baseline to post-baseline visits and Week 24 endpoint.

Change from baseline to Week 24 endpoint in vital signs and physical characteristics will be summarized for patients who have both a baseline and at least one post-baseline result. Baseline is defined as the last non-missing result on or prior to the date of the first injection of study treatment.

Change from the minimum value on or prior to the date of the first injection of study treatment to the minimum value during the Treatment Period in vital signs and physical characteristics will be summarized for patients who have both a baseline and at least one post-baseline result. Similarly, change from the maximum value on or prior to the date of the first injection of study treatment to the maximum value during the Treatment Period in vital signs and physical characteristics will be summarized for patients who have both a baseline and at least one post-baseline result. Scheduled visits, unscheduled visits, and repeat measurements will be included.

The percentages of patients with treatment-emergent high or low vital signs and physical characteristics at any time during the Treatment Period will be summarized. Similarly, the percentages of patients with treatment-emergent high or low vital signs and physical

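### Several SAP safety and biomarker sections cut baseline at the date of the first infusion, not before the dose, so an unscheduled post-infusion Day 1 value could be taken as baseline.

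*SAP*

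**What the plan says.** The plan carries two baseline rules.

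The first is tied to the dose. The Baseline row in SAP 4.1 reads "Defined as the last available value before the first dose of study intervention for both efficacy and safety analyses", and protocol 9.4.1 has the same rule.

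The second is tied to the calendar date. The text of SAP 4.1 has baseline for the Treatment Period "defined as the last non-missing assessment on or prior to the date of the first injection of study treatment". SAP 4.6.3 repeats it for laboratory tests: "baseline is defined as the last non-missing result on or prior to the date of the first injection of study treatment". SAP 4.6.4.2 does so for immunoglobulins and cytokines: "Baseline is defined as the last non-missing result on or prior to the date of the first injection of study treatment". SAP 4.6.4.3 (receptor occupancy, soluble PD-1, biomarkers) and 4.6.5 (vital signs) use the same cut-off. SAP 4.6.4.1 averages the flow cytometry results up to and including that date. None of these gives a time of day.

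SAP 4.6.3 and 4.6.5 also plan extreme-value summaries, worded in 4.6.5 as "Change from the minimum value on or prior to the date of the first injection of study treatment to the minimum value during the Treatment", with a matching analysis of maxima. Both state that unscheduled and repeat values count.

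Two other sentences in SAP 4.1 point back to the dose: "The baseline period is defined as Visit 1 through pre-dose Visit 2", and "Any assessment collected after the first injection through the date of the Week 12 or early discontinuation visit is defined as post-baseline". SAP 4.9 declares no change from the protocol's analyses, so the date rule is not presented as a deliberate departure.

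**The concern.** A date cut-off and a dose cut-off differ only for values recorded later on the day of the first infusion. Those are the values most likely to exist because something happened. Protocol 2.3 names infusion-related hypersensitivity and cytokine release as risks of this kind of product. If a reaction value is used as the participant's reference, the rise or fall caused by the reaction is not shown as an on-treatment change. The later return to the usual level then looks like a change in the opposite direction.

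What is at stake is the accuracy of some descriptive change-from-baseline displays: laboratory tests, vital signs, cytokines and related biomarkers.

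**Working it through.** The plan states no figure that depends on this definition, so there is nothing to reproduce. The check is a comparison of the texts, followed by an illustration.

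**1. The definitions side by side**

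| Place | Cut-off | Unscheduled values |
|---|---|---|
| Protocol 9.4.1; SAP 4.1 Baseline row | before first dose | not stated |
| SAP 4.1 text | date of first injection | not stated |
| SAP 4.6.3 laboratory | date | included in minimum/maximum |
| SAP 4.6.4.1 flow cytometry | date, average | included |
| SAP 4.6.4.2 immunoglobulins, cytokines | date | not stated |
| SAP 4.6.4.3 receptor occupancy, soluble PD-1, biomarkers | date | not stated |
| SAP 4.6.5 vital signs | date | included in minimum/maximum |
| SAP 4.6.2 AE severity | before first injection | not applicable |

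**2. Which rule governs.** The Baseline row applies unless the SAP indicates otherwise, and the SAP 4.1 text applies unless otherwise specified. Sections 4.6.3 to 4.6.5 do specify, and they use the date. A programmer working from those sections would compare dates. The SAP 4.1 sentence that classes later assessments as post-baseline does not remove a later Day 1 value from baseline, so the same value satisfies both descriptions.

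**3. Which Day 1 values can follow the infusion.** The Schedule of Activities places the Day 1 hematology, chemistry, hsCRP, flow cytometry, cytokine and immunoglobulin samples before dosing, and vital signs before blood sampling. Only unscheduled values are exposed. The protocol allows three sources:
- extra vital signs at the investigator's discretion (8.2.2), with monitoring during and for at least 1 hour after the infusion (6.1);
- additional laboratory tests (10.2);
- the hypersensitivity work-up in Appendix 6, which lists a cytokine panel: "Collect sample after the participant has been stabilized, and within 1 to 2 hours of the event", or as late as 12 hours.

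**4. Effect on a change from the last value.** Assume a pre-dose value of 1, a post-infusion Day 1 value of f that is the last that day, and a later value of 1. The factor f is an assumption, because the documents give none.
- Pre-dose baseline: percent change at the later visit = 100(1 - 1)/1 = 0%.
- Date baseline: percent change = 100(1 - f)/f = 100(1/f - 1).
- Shift in the arm mean from one such participant = 100(1/f - 1)/n.

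| f | Participant, date rule | Arm mean, n = 20 | Arm mean, n = 40 |
|---|---|---|---|
| 1.5 | -33.3% | -1.67 | -0.83 |
| 2 | -50% | -2.5 | -1.25 |
| 5 | -80% | -4.0 | -2.0 |
| 10 | -90% | -4.5 | -2.25 |

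**5. Effect on maximum-to-maximum change.** This applies to laboratory tests and vital signs whether or not the reaction value is the last that day. With the same sequence and f = 10, a pre-dose baseline gives 10 - 1 = +9. SAP 4.1 starts the double-blind period after the first injection, so read literally the Day 1 value counts on both sides and the change is 10 - 10 = 0. If it is kept only as baseline, the change is 1 - 10 = -9. A low value acts on the minimum in the same way.

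Participants without an unscheduled post-infusion Day 1 value have the same baseline under both rules.

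**The case against.** The strongest reply is that SAP 4.1, read as a whole, already intends a pre-dose baseline. It ends the baseline period before dosing, places the first injection at the end of Visit 2, and calls anything afterwards post-baseline. This stands against the inference that reaction values do become the baseline: the documents leave an ambiguity, not a settled rule. It does not clear the later sections, which restate the date rule without those limits.

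The second reply is that little is exposed, and this stands:
- A first-infusion reaction remains a treatment-emergent event under SAP 4.6.2, and SAP 4.6.2.1 summarises hypersensitivity by severity and timing. A reader might infer that the reaction vanishes from the safety report, but it does not.
- Efficacy assessments on Day 1 precede dosing, so no efficacy endpoint moves.
- Appendix 6 sampling follows generalised urticaria or suspected anaphylaxis, and its tests are optional. It lists no flow cytometry, immunoglobulins, receptor occupancy or soluble PD-1, and SAP 4.6.4.2 does not say whether unscheduled cytokine values count.

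Third, a reader might infer that a low blood pressure during a reaction necessarily becomes the reference for the limits in SAP Table 2. Table 2 uses change from baseline, and baseline is the last value. With monitoring for at least 1 hour, a recovered reading may be the last that day. The baseline minimum belongs to a separate summary.

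Fourth, the reaction rate is unknown. Protocol 2.2 and 2.3 report 47 + 6 + 7 = 60 people exposed in two other studies without clinically significant safety concerns, infusion reactions included. That is not a count of reactions, and the populations and some doses differ, but it gives no reason to expect many.

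**Conclusion.** Wrong as written; minor. The dose-based and date-based definitions contradict each other within SAP 4.1, and the date-based one is repeated in five later subsections (4.6.3, 4.6.4.1, 4.6.4.2, 4.6.4.3 and 4.6.5). Applied literally, it could make an unscheduled post-infusion Day 1 value the baseline when it is the last that day. For laboratory tests and vital signs it would put that value among the candidates for the baseline minimum or maximum in any case. The numerical change would then be understated or reversed in participants with a first-infusion reaction that produced such a value.

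No trial-level figure changes. The shifts of -4.5 points (n = 20) and -2.25 points (n = 40) assume one participant in the arm, a 10-fold rise, a later return to the pre-dose level, and a Day 1 reaction sample used as baseline. A reader might also infer that the bias falls mainly on the LY3462817 arms. That is plausible for drug reactions, but the documents give no reaction rates by arm, so it remains conjecture.

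**What to change.** In SAP 4.1 (text), 4.6.3, 4.6.4.1 to 4.6.4.3 and 4.6.5, replace the date cut-off with: before the start of the first infusion (date and time). This restores the rule in protocol 9.4.1 and the SAP's own Baseline row.

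Add that Day 1 values timed after the start of the infusion, including event-driven hypersensitivity samples, are post-baseline and never enter a baseline value, average, minimum or maximum. Where a time is missing, treat scheduled Visit 2 assessments as pre-dose and unscheduled Day 1 assessments as post-dose. That convention may misplace an untimed repeat taken before dosing, which is a small price for a fixed rule.

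The cost is SAP wording and one programming condition. Dose date and time are already recorded (protocol 6.4), and Appendix 6 requires the time of each hypersensitivity sample. The change should be made before any unblinding.
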